### 6.1.3 Dose Escalation

[Section 4.1.](#)

#### **6.1.4 Dose Modifications**

No dose modifications.

##### **Diluent: 0.9% NaCl for injection, USP**

Will be provided by DMID via the DMID CMS.

All study products will be shipped to the clinical research site upon request and approval from DMID.

#### **Accountability**

The participating site PI is responsible for study product distribution and disposition and has ultimate responsibility for study product accountability. The participating site PI may delegate to the participating site's research pharmacist responsibility for study product accountability. The participating site's research pharmacist will be responsible for maintaining complete records and documentation of study product receipt, accountability, dispensation, storage conditions, and final disposition of the study product(s). Study product accountability records and dispensing logs should include, but are not limited to the following: DMID protocol number; name, dosage form, strength of the study product; capture vial numbers assigned sequentially by the pharmacists as vials/syringes are used (number uniquely, do not start over at 1 or repeat numbers), manufacturer or other source; control, lot number or other identification number; expiration or retest date; date of receipt of the study product; quantity received from supplier; subject identification number; quantity dispensed as amount or dose per subject; balance of study product currently available; disposition of study product if not dispensed to a study subject (e.g., disposed/destroyed or returned to supplier as per protocol or protocol-specific MOP or as directed by DMID); date of vaccine preparation/administration, time of vaccine preparation, expiration of vaccine preparation; and amount of vaccine withdrawn for administration. Time of vaccine administration to the subject will be recorded on the appropriate data collection form (DCF). All study product(s), including the amount of mRNA-1273, diluent (0.9% NaCl for injection, USP), and vial admixtures, whether administered or not, must be documented on the appropriate study product accountability record or dispensing log. The sponsor's monitoring staff will verify the

participating site's study product accountability records and dispensing logs per the DMID-approved clinical monitoring plan (CMP).

Once all subject dosing is complete, the pharmacy staff should retain or dispose of used study products and complete study product accountability procedures in accordance with site-specific standard operating procedures (SOPs). This applies to:

- used and unused mRNA-1273 vials
- used mixing vials
- mRNA-1273 cartons

All used supplies noted above may either be sequestered from the unused supplies and retained until study conclusion or until study product accountability has occurred by the monitor and written notification stating retention is no longer required is received, or may be destroyed in accordance with site-specific SOPs with a second pharmacy staff member's observation and verification as documented in the pharmacy log. Refer to the protocol-specific MOP for details on storing used mRNA-1273 vials, used 0.9% NaCl Injection vials and used mixing vials.

### **Destruction**

After the study treatment period has ended or as appropriate over the course of the study after study product accountability has been performed, disposition of unused and used mRNA-1273 vials should occur as noted:

- Unused and Used mRNA-1273 vials:
  - Should be destroyed on-site following applicable site procedures or by the site's selected destruction vendor. Following the site's procedure for the destruction of hazardous material or study product destruction policy/SOP when destroying used and unused items.
  - A certificate of destruction or documentation of destruction should be provided to the sponsor and retained in the Pharmacy Binder once completed.

Used syringes may be destroyed in accordance with site-specific SOPs.

### **6.2.2 Formulation, Appearance, Packaging, and Labeling**

#### **Product: mRNA-1273**

mRNA-1273 is provided as a sterile liquid for injection, white to off white dispersion in appearance, at a concentration of 0.5 mg/mL in 20 mM Tris buffer containing 87 mg/mL sucrose and 10.7 mM sodium acetate, at pH 7.5.

#### **Diluent: 0.9% NaCl for injection, USP**

The USP grade 0.9% NaCl or normal saline for injection is a sterile, nonpyrogenic, isotonic solution; each mL contains NaCl 9 mg. It contains no bacteriostatic agent, antimicrobial agent, preservatives, or added buffer and is supplied only in single-dose containers. It is clear in appearance, and available in 10 mL vials.

Each of the study products will be labeled according to manufacturer specifications and include the statement "Caution: New Drug Limited by Federal Law to Investigational Use."

Sterile empty vials (2-mL or 10-mL) will be provided with latex-free stoppers.

### **6.2.3 Product Storage and Stability**

#### **Product: mRNA-1273**

mRNA-1273 is stored at -70°C (-60°C to -90°C).

Stability protocols for mRNA-1273 will include at least 24-months duration at the intended storage temperature (-60°C to -90°C).

Stability and compatibility with the apparatus intended for administration for up to 8 hours after preparation were assessed. The prepared doses were stable for clinical in-use for up to 8 hours at room temperature (**Note: up to 4 hours at room temperature for 10 mcg doses**).

#### **Diluent: 0.9% NaCl for injection, USP**

0.9% NaCl for injection, USP is stored at 20 to 25°C (68 to 77°F) [See USP Controlled Room Temperature.]

The temperature of the storage unit must be manually recorded daily (excluding non-business days and holidays, as applicable) and continuously monitored and recorded during the course of this trial per site-specific SOPs, and documentation will be maintained. If the temperature fluctuates outside of the required range, the affected study product(s) must be quarantined at the correct storage temperature and labeled as 'Do Not Use' (until further notice). The participating site's research pharmacist must alert the participating site PI and study coordinator, if the temperature fluctuates outside of the required range. In the event the temperature fluctuates outside of the required range, including accidental deep-freezing or disruption of the cold chain, the affected study product(s) must not be administered. The participating site PI or responsible person should immediately contact the DMID Product Support Team at [[contact]](mailto:[contact]) for further instructions before any additional vaccinations are administered. Based on the information collected, DMID and/or the manufacturer will determine whether the affected study product(s) can be used. If it cannot be used, the participating site will receive specific instructions on how to return the affected study product(s) to the DMID CMS or destroy it on-site. Additional instructions for quarantine and DMID contact information are provided in the protocol-specific MOP.

mRNA-1273 must be stored in a secure area with limited access (pharmacy staff only), and must be stored frozen at -60°C to -90°C. The freezer should have an automated temperature recording and alert system. There must be an available back-up freezer. The freezers must be connected to a back-up generator; or alternate plan in the event of a power failure. The pharmacy must have in place a 24-hour alert system that allows for rapid response in case of freezer malfunctioning. In addition, vaccine accountability study staff (e.g., pharmacy staff) are required to keep a temperature log to establish a record of compliance with these storage conditions. Only vaccine accountability study staff (e.g., pharmacy staff) should have access to the product used in this study. The participating site is responsible for reporting any mRNA-1273 that was not temperature controlled during shipment or during storage to the pharmacy staff. Such mRNA-1273 will be retained for inspection by the pharmacy staff and disposed of according to approved methods.

### **6.2.4 Preparation**

Refer to the protocol-specific MOP for details about preparation.

## **6.3 Measures to Minimize Bias: Randomization and Blinding**

### **6.3.1 Treatment Assignment Procedures**

Per International Council for Harmonisation of Technical Requirements for Pharmaceuticals for Human Use (ICH) guideline E6: GCP, screening records will be kept at the participating site to document the reason why an individual was screened, but failed trial entry criteria. The reasons why individuals failed screening will be recorded in the Statistical and Data Coordinating Center's (SDCC) Advantage eClinicalSM (Electronic Data Capture System).

Once consented and upon entry of demographic data and confirmation of eligibility for this trial, the subjects will be enrolled. Enrollment will proceed in a staged fashion. Sentinel subject dosing will begin with 4 subjects in cohort 1 (25 mcg). The 4 sentinel subjects for cohort 2 (100 mcg) will be enrolled no earlier than one day after enrollment of the last of the 4 sentinel subjects in cohort 1. If no halting rules have been met after the 8 sentinel subjects have completed Day 5, then full enrollment will proceed first with the remaining subjects in cohort 1, followed by the remaining subjects in cohort 2 without interruption. If no halting rules have been met after all subjects in cohort 2 have completed Day 8, then dosing of 4 sentinel subjects will begin in cohort 3. If no halting rules have been met after the 4 sentinel subjects in cohort 3 have completed Day 5, then full enrollment of cohort 3 will proceed.

If no halting rules have been met after all subjects in cohorts 1 and 2 have completed Day 8, dosing will begin for cohorts 4 (25 mcg; 56-70 years of age) and 5 (100 mcg; 56-70 years of age). If no halting rules have been met after all subjects in cohorts 4 and 5 have completed Day 8, dosing will begin for cohorts 7 (25 mcg;  $\geq 71$  years of age) and 8 (100 mcg;  $\geq 71$  years of age).

Based on the interim immunogenicity data available as of May 15, 2020, enrollment into cohorts 6 and 9 (250 mcg; 56-70 years of age and  $\geq 71$  years of age) will be deferred in order to explore lower dosages. Therefore, enrollment of cohorts 10-12 (50 mcg; 18-55 years of age, 56-70 years of age and  $\geq 71$  years of age) will be prioritized. Subjects will be enrolled simultaneously in cohorts 10-12; there will be no staging. To further explore dosage sparing, cohort 13 (10 mcg dose; 18-55 years of age) may be enrolled. A decision regarding the enrollment of cohorts 6, 9 and 13 will be made after review of interim immunogenicity data from cohorts 1-5, 7, 8, and 10-12.

If no halting rules have been met after all subjects in cohorts 5 and 8 have completed Day 8, dosing will begin concurrently for cohorts 10-12. If no halting rules have been met after all subjects in cohorts 3, 7 and 8 have completed Day 8, dosing may begin for cohort 6, if enrolled. If no halting rules have been met after all subjects in cohort 6 have completed Day 8, dosing may begin for cohort 9, if enrolled.

### **6.3.2 Randomization and Blinding**

This is an open-label study with sequential group enrollment so randomization and blinding will not be utilized.

### **6.3.3 Blinding and Masking Procedures**

Not Applicable

## **6.4 Study Intervention Compliance**

Each dose of study product will be administered by a member of the clinical research team that is qualified and licensed to administer the study product. Administration and date, time, and location of injection will be recorded on the appropriate DCF.

## **6.5 Concomitant Therapy**

Information about prior medications, including hormonal contraceptives, taken by the subject in the 30 days prior to providing informed consent will be recorded on the appropriate DCF.

Concomitant medications include all medications (prescription, over the counter, supplements, and vaccines received outside of the study) taken by the subject from the time the informed consent is signed through Day 394. At each study visit following dosing, including telephone calls, subjects will be queried about new concomitant medications and changes to existing medications.

Medications that might interfere with the evaluation of the investigational product should not be used by the subject during the study-reporting period (12 months after the second vaccination) unless clinically indicated as part of the subject's health care.

In the event medical conditions dictate the use of medications, subjects are encouraged to obtain adequate care, comply with the course of therapy as prescribed by their physician, and inform the study Investigator as soon as practical. Any drug or vaccine used or received by the subject during the trial should be recorded on the appropriate DCF.

### **6.5.1 Rescue Medicine**

Not Applicable

### **6.5.2 Non-Research Standard of Care**

Not Applicable

## **7. STUDY INTERVENTION DISCONTINUATION AND SUBJECT DISCONTINUATION/WITHDRAWAL**

### **7.1 Halting Criteria and Discontinuation of Study Intervention**

#### **7.1.1 Halting Criteria**

The study will be paused if any of the following events occur:

- 1- Any subject experiences an SAE after administration of the vaccine that is considered related to vaccine.
- 2- Any subject experiences laryngospasm, bronchospasm or anaphylaxis within 24 hours after administration of vaccine that is considered related to vaccine.
- 3- Any subject experiences ulceration, abscess or necrosis at the injection site that is considered related to vaccine administration.

- 4- Two (2) or more subjects experience an allergic reaction such as generalized urticaria (defined as occurring at three or more body parts) within 72 hours after administration of vaccine that is considered related to vaccine.
- 5- Three (3) or more subjects experience a Grade 3 AE (unsolicited and/or clinical laboratory abnormality), in the same Preferred Terms based on the Medical Dictionary for Regulatory Activities (MedDRA) coding, that lasted at least 48 hours after administration of the vaccine and is considered related to the vaccine. Clinical laboratory abnormalities are not subject to the time window.

Study product administration and enrollments may resume only after review of the AEs that caused the pause results in a recommendation to permit further study product administration and enrollments.

### **7.1.2 Sentinel Halting Criteria**

If any of the following events occur to the sentinel subjects, the study will be paused:

- 1- Any subject experiences ulceration, abscess or necrosis at the injection site.
- 2- Any subject experiences laryngospasm, bronchospasm or anaphylaxis within 24 hours after administration of vaccine.
- 3- Any subject experiences generalized urticaria (defined as occurring at three or more body parts) within 72 hours after administration of vaccine.
- 4- Any subject experiences an SAE (except for accident or trauma) after administration of the vaccine that is considered related to the vaccine.
- 5- Any 2 subjects in the same cohort experience the same Grade 3 Solicited Local AE or Systemic AE, (excluding measured grades of erythema and edema/induration alone) that lasted at least 48 hours within 7 days after administration of the vaccine.
- 6- Any 2 subjects experience the same Grade 3 AE (unsolicited and/or clinical laboratory abnormality), in the same Preferred terms based on the MedDRA coding, that lasted at least 48 hours after administration of the vaccine and is considered related to the vaccine. Clinical laboratory abnormalities are not subject to the time window.

### **7.1.3 Criteria for Continuation of Dosing and Redosing**

In the event a halting rule is met:

- an unscheduled safety analysis by the SMC will be required for approval of further enrollment, and
- further administration of the vaccine, including a second dose, is suspended for ALL subjects until an assessment by the SMC takes place.

#### **7.1.3.1 Withdrawal Criteria for Second Study Vaccination**

Prior to receiving the second vaccination, subjects will be reassessed. The following events constitute contraindications to any further administration of vaccines. If any of these events occur during the study, the subject must not receive the second vaccination but will be

encouraged to continue study participation for safety and immunogenicity evaluations through 12 months after their last vaccination.

- Withdrawal of consent.
- As deemed necessary by the participating site PI or appropriate sub-investigator for non-compliance or other reasons. This may include previously undisclosed or new conditions that meet exclusion criteria.
- Any clinically significant medical condition that, in the opinion of the participating site PI or appropriate sub-investigator, poses an additional risk to the subject if he/she continues to participate in the study.
- Anaphylaxis or unexpected systemic hypersensitivity reaction following the administration of the first vaccination.
- Any SAE judged to be related to vaccine.
- Pregnancy.
- Subject is lost to follow-up.
- New information becomes available that makes further participation unsafe.
- Termination of this trial.

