## 3. OBJECTIVES AND ENDPOINTS

**Table 5: Objectives and Endpoints (Outcome Measures)**

OBJECTIVES	ENDPOINTS (OUTCOME MEASURES)
Primary	

 
To evaluate the safety and reactogenicity of a 2-dose vaccination schedule of mRNA-1273, given 28 days apart, across 5 dosages in healthy adults.
 
	
 
Frequency and grade of each solicited local and systemic reactogenicity AE during a 7-day follow-up period post each vaccination.
 
Frequency and grade of any unsolicited AEs during the 28-day follow-up period post each vaccination.
 
Frequency of any SAEs, Protocol Specified AESIs, NOCMCs, and MAAEs from Day 1 to Day 394.
 

Secondary	

 
To evaluate the immunogenicity as measured by IgG ELISA to the SARS-CoV-2 S (spike) protein following a 2-dose vaccination schedule of mRNA-1273 at Day 57.
 
	
 
GMT of antibody at Day 57.
 
Percentage of subjects who seroconverted, defined as a 4-fold change in antibody titer from baseline.
 
The GMFR in IgG titer from baseline.
 

Exploratory	

OBJECTIVES	ENDPOINTS (OUTCOME MEASURES)

 
To evaluate the immunogenicity as measured by IgG ELISA to the SARS-CoV-2 S (spike) protein following a 2-dose vaccination schedule of mRNA-1273 at all timepoints, other than Day 57.
 
	
 
GMT of antibody at each timepoint.
 
Percentage of subjects who seroconverted at each timepoint.
 
The GMFR in IgG titer from baseline at each post-vaccination timepoint.
 

 
To evaluate the immunogenicity as measured by IgM and IgA ELISA to the SARS-CoV-2 S (spike) protein following a 2-dose vaccination schedule of mRNA-1273 given 28 days apart.
 
	
 
GMT at each timepoint.
 
Percentage of subjects who seroconverted at each timepoint.
 
The GMFR in IgM and IgA titer from baseline at each post-vaccination timepoint.
 

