**Table 6: Treatment Arms**

Cohort	Sample Size	Stratum (Years of Age)	First and Second Dose
1	15	18-55	25 mcg mRNA-1273
2	15	18-55	100 mcg mRNA-1273
3	15	18-55	250 mcg mRNA-1273
4	10	56-70	25 mcg mRNA-1273
5	10	56-70	100 mcg mRNA-1273
6*	10	56-70	250 mcg mRNA-1273
7	10	$\geq 71$	25 mcg mRNA-1273
8	10	$\geq 71$	100 mcg mRNA-1273
9*	10	$\geq 71$	250 mcg mRNA-1273
10	15	18-55	50 mcg mRNA-1273
11	10	56-70	50 mcg mRNA-1273
12	10	$\geq 71$	50 mcg mRNA-1273
13*	15	18-55	10 mcg mRNA-1273

\*Cohorts 6, 9 and 13 were not enrolled.

Up to one hundred and fifty-five (155) subjects will be enrolled into one of thirteen cohorts (10 mcg, 25 mcg, 50 mcg, 100 mcg, or 250 mcg). Subjects will receive an IM injection (0.5 mL) of mRNA-1273 on Days 1 and 29 in the deltoid muscle and will be followed through 12 months post second vaccination (Day 394). The second dose of vaccine (0.5 mL) will be administered preferably in the same arm used for the first dose.

Follow-up visits will occur 1, 2 and 4 weeks post each vaccination (Days 8, 15, 29, 36, 43, and 57), as well as 3, 6 and 12 months post second vaccination (Days 119, 209 and 394).

Reactogenicity will be assessed at these visits, as well as blood will be drawn for immunogenicity assays. Additional safety and reactogenicity data will be solicited via telephone calls to subjects 1 and 2 days post each vaccination (Days 2, 3, 30, and 31).

To determine early safety signals for this phase I clinical trial, vaccination will proceed in a staged fashion. Sentinel subject dosing will begin with 4 subjects in cohort 1 (25 mcg). The 4 sentinel subjects for cohort 2 (100 mcg) will be enrolled no earlier than one day after enrollment of the last of the 4 sentinel subjects in cohort 1. If no halting rules have been met after the 8 sentinel subjects have completed Day 5, then full enrollment will proceed first with the remaining subjects in cohort 1, followed by the remaining subjects in cohort 2 without interruption. If no halting rules have been met after all subjects in cohort 2 have completed Day 8, then dosing of 4 sentinel subjects will begin in cohort 3. If no halting rules have been met after the 4 sentinel subjects in cohort 3 have completed Day 5, then full enrollment of cohort 3 will proceed.

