## 4.4 Optional Third mRNA-1273 Vaccination Substudy

All subjects in this clinical trial were scheduled to receive two mRNA-1273 vaccinations, 28 days apart, at dosages of 25, 50, 100, or 250 mcg (see [Table 1](#)), with the last scheduled follow-up visit occurring at 365 days after the second vaccination (see [Table 4](#)). During the course of the main study, interim efficacy data from a Phase 3 placebo-controlled clinical trial of mRNA-1273 (COVE), administered as 2 doses of 100 mcg given 28 days apart, demonstrated vaccine efficacy of 94.1% (95% CI: 89.3%, 96.8%) for the prevention of symptomatic, confirmed COVID-19

(Baden, LR, et al. 2020). After review of the interim safety and efficacy data from that clinical trial, the FDA granted on December 18, 2020 an Emergency Use Authorization (EUA) for the mRNA-1273 vaccine in adults 18 years of age and older.

To potentially enhance and extend the duration of protection provided by the 2-dose vaccination schedule of mRNA-1273 administered in the main study, and to gain an understanding of the immune responses to a third dose of mRNA-1273, subjects in the main study may participate in an optional third mRNA-1273 vaccination substudy, detailed in [Section 12, Appendix A](#). Substudy subjects will receive a third mRNA-1273 vaccination, administered via an IM injection at a dosage of 100 mcg/0.5 mL, given six to twelve months after receipt of their second vaccination in the main study. Substudy subjects will be followed for safety, reactogenicity, and immunogenicity endpoints through 12 months post third vaccination (Substudy Day 366).

To be eligible to participate in the substudy, subjects must have received both the first and second mRNA-1273 vaccinations in the main study. Other eligibility criteria are specified in [Appendix A](#). Subjects who received only one mRNA-1273 vaccination in the main study will be advised to receive an FDA authorized or approved COVID-19 vaccine, according to the recommended schedule, when available to them outside of this trial, unless they have a contraindication to COVID-19 vaccines that are available.

Subjects who elect not to participate in the optional third mRNA-1273 vaccination substudy or are not eligible for the substudy will continue to be followed according to the Schedule of Activities for the main study (see [Table 4](#)) with the Final Study Visit 14 occurring at Day 394 ( $\pm 14$  days).

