#### **7.1.4 Follow-up for Subjects that Discontinued Study Intervention**

Discontinuation of study intervention does not require discontinuation from the study, and the remaining study procedures should be completed as indicated by the SOA. If a clinically significant finding is identified, including, but not limited to, changes from baseline, after enrollment, the participating site PI or qualified designee will determine if any change in subject management is needed. Any new clinically relevant finding will be reported as an AE.

The data to be collected at the time of study intervention discontinuation should include the following:

- Clinical safety laboratory evaluations.
- Complete physical examination.

- Vital signs (BP, heart rate [HR], oral temperature).
- Immunogenicity evaluations.

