## 7.2 Subject Withdrawal from the Study and Replacement

Subjects are free to withdraw from participation in the study at any time upon request, without any consequence.

A study subject will be discontinued from participation in the study if any of the following reasons occur prior to initial dosing:

- Request by the subject to terminate participation.
- Vaccine is not administered.

A subject may be removed from the study for the following reasons post initial dosing; however, whenever possible the subject should be followed for safety and immunogenicity evaluations per protocol:

- Subject becomes pregnant before receiving the second dose of vaccine.
- Study non-compliance to protocol requirements that in the opinion of the participating site PI or appropriate sub-investigator poses an increased risk (e.g., missing safety labs) or compromises the validity of the data.
- Lost to follow-up.
- If the subject met an exclusion criterion for participation in the study (either newly developed or not previously recognized) that precludes further study participation.
- Request of primary care provider; the IRB, FDA, or NIAID.
- Medical disease or condition, or new clinical finding(s) for which continued participation, in the opinion of the participating site PI or appropriate sub-investigator might compromise the safety of the subject, interfere with the subject's successful completion of this study, or interfere with the evaluation of responses.
- If any AE, clinical laboratory abnormality or situation occurs such that continued participation in the study would not be in the best interest of the subject.
- The occurrence of an SAE.

If the subject agrees, every attempt will be made to follow all AEs through resolution or stabilization.

Subjects who withdraw, or are withdrawn from this study, or are lost to follow-up after signing the informed consent form (ICF) and administration of the study product will not be replaced.

Subjects who withdraw, or are withdrawn from this study, or are lost to follow-up after signing the ICF but before administration of the study product may be replaced.

The reason for subject discontinuation or withdrawal from the study will be recorded on the appropriate DCF.

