## 12.5 Study Design

This is a substudy to a phase I, open-label, dose-ranging clinical trial to assess a third mRNA-1273 vaccination, administered via an IM injection at a dosage of 100 mcg/0.5 mL, in subjects, 18 years of age and older, who received both the first and second mRNA-1273 vaccinations in the main study (see [Table 13](#)) and meet all other substudy eligibility criteria. This optional third mRNA-1273 vaccination substudy is designed to assess safety, reactogenicity, and immunogenicity through 12 months post third vaccination (Substudy Day 366). Subjects who participate in this substudy are from the same three domestic clinical research sites that enrolled into the main study.

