**Table 13: Treatment Arms and Substudy Dosing**

Cohort	Sample Size**	Stratum (Years of Age)	First and Second Dose in Main Study	Optional Third Dose in Substudy
1	15	18-55	25 mcg mRNA-1273	100 mcg mRNA-1273
2	15	18-55	100 mcg mRNA-1273	100 mcg mRNA-1273
3	15	18-55	250 mcg mRNA-1273	100 mcg mRNA-1273
4	10	56-70	25 mcg mRNA-1273	100 mcg mRNA-1273
5	10	56-70	100 mcg mRNA-1273	100 mcg mRNA-1273
6*	10	56-70	250 mcg mRNA-1273	n/a
7	10	≥71	25 mcg mRNA-1273	100 mcg mRNA-1273
8	10	≥71	100 mcg mRNA-1273	100 mcg mRNA-1273
9*	10	≥71	250 mcg mRNA-1273	n/a
10	15	18-55	50 mcg mRNA-1273	100 mcg mRNA-1273
11	10	56-70	50 mcg mRNA-1273	100 mcg mRNA-1273
12	10	≥71	50 mcg mRNA-1273	100 mcg mRNA-1273
13*	15	18-55	10 mcg mRNA-1273	n/a

\*Cohorts 6, 9 and 13 were not enrolled.

\*\*\*Four subjects did not receive the second dose of mRNA-1273 in the main study. Three subjects discontinued due to an AE (hives on lower extremities judged related to the first mRNA-1273 vaccination [cohort 1], sore throat [cohort 3], and maculopapular rash [cohort 5]); the other subject discontinued treatment due to quarantine for a COVID-19 exposure (cohort 1).

The third mRNA-1273 vaccination will be offered to subjects who received 2 doses of 25 or 50 mcg (cohorts 1, 4, 7, 10, 11, and 12), which are lower than the EUA mRNA-1273 dosage of 100

mcg, as soon as feasible after their Main Study Day 209 visit, and also will be offered to subjects who received 2 doses of 100 and 250 mcg (cohorts 2, 3, 5, and 8) no later than the close of the window for their originally scheduled Main Study Day 394 visit.

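### For one-dose subjects, Section 7.1.3.1 points to Day 366 against the Day 394 safety endpoint, and Section 7.2 allows an SAE or pregnancy alone to remove a subject from the study

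*Protocol*

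**What the plan says.** **Length of follow-up after a missed Dose 2.** Section 7.1.3.1 lists the events that bar the second vaccination and says that such subjects will be "encouraged to continue study participation for safety and immunogenicity evaluations through 12 months after their last vaccination". Section 7.1.4 says: "Discontinuation of study intervention does not require discontinuation from the study, and the remaining study procedures should be completed as indicated by the SOA". Section 4.4 makes both main-study doses a condition of entering the substudy. It then keeps everyone not eligible for the substudy on the main schedule, "with the Final Study Visit 14 occurring at Day 394". Sections 8.3.1, 8.3.1.2 and 8.3.5 collect SAEs, AESIs, MAAEs and NOCMCs to Day 394, with no exception for one-dose subjects. The third primary endpoint in Table 5 is "Frequency of any SAEs, Protocol Specified AESIs, NOCMCs, and MAAEs from Day 1 to Day 394".

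**Removal from the study.** Section 7.2 lists reasons for which a subject may be removed after the first dose. One is "The occurrence of an SAE", with no condition on relatedness or on the subject's interest. Another is pregnancy before the second dose. Section 7.1.3.1 treats a vaccine-related SAE and pregnancy as bars to further dosing, with participation continuing.

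**Who is affected.** The footnote to Table 13 records: "Four subjects did not receive the second dose of mRNA-1273 in the main study". Three stopped because of an AE (cohorts 1, 3 and 5) and one because of quarantine after a COVID-19 exposure (cohort 1).

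**The concern.** A site handling a subject who misses Dose 2 has two end dates for the same person. If it follows Section 7.1.3.1, observation ends before the endpoint period does and before the final scheduled visit can take place. If it follows Section 7.1.4 or 4.4, the subject stays to Visit 14. Section 7.2 raises a similar question for a subject who has an SAE or becomes pregnant before Dose 2: the text does not say whether someone removed on that ground keeps the safety schedule to Day 394.

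Both rules act on subjects selected largely by an event. The analysis would not correct for shortened observation. One-dose subjects belong to the Safety population (Protocol Section 9.3, SAP Section 6.2.3), AE incidence is taken over the total population (SAP Section 9.3), and nothing is imputed (SAP Section 6.4). A subject no longer observed therefore counts as event-free, so a missed first event would lower the reported frequency.

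**Working it through.** **Inputs.** Dose 1 on Day 1. Visit 06 (Dose 2) on Day 29 ± 2. Visit 13 on Day 209 ± 7 and Visit 14 on Day 394 ± 14, both counted from the actual Visit 06 date (Table 4 and its notes). 120 subjects enrolled (Section 12.2), 4 of them one-dose (Table 13 footnote).

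**The plan's own figure.** Twelve months after Dose 2 is 29 + 365 = Day 394, as Section 4.1 states. The same count from a Day 1 dose is 1 + 365 = Day 366, which is the convention of Section 12.5 (Substudy Day 366).

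**End date for a one-dose subject under Section 7.1.3.1.** The last vaccination is Dose 1, so the end is Day 366.
- Shortfall against the endpoint: 394 − 366 = 28 days; 28/394 = 7.1%.
- Opening of Visit 14 = Visit 06 day + 365 − 14:

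| Visit 06 | Visit 14 opens | Days after Day 366 |
|---|---|---|
| Day 27 | Day 378 | 12 |
| Day 29 | Day 380 | 14 |
| Day 31 | Day 382 | 16 |

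Day 366 precedes Visit 14 for every permitted Visit 06 date. The last routine visit before it is Visit 13, 366 − 209 = 157 days earlier.

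**Size across the trial.** If all four one-dose subjects ended at Day 366, the loss would be 4 × 28 = 112 person-days out of 120 × 394 = 47,280, or 0.24%. The four are 4/120 = 3.3% of subjects.

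**Effect on the detection probabilities.** Section 9.2 assumes that subjects complete their safety visits and uses 1 − (1 − p)^n. Its figures reproduce: n = 15, p = 20% gives 96.5% (stated as about 97%), and n = 60, p = 5% gives 95.4% (stated as at least 95%). Without the one-dose subjects (two in cohort 1, one in cohort 3):
- cohort 1, n = 13, p = 20%: 94.5%, down from 96.5%;
- ages 18-55, n = 57, p = 5%: 94.6%, down from 95.4%.

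These falls apply only to events that would be seen in the missed period.

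**Removal rules side by side.**

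| Event | Sections 7.1.3.1 and 7.1.4 | Section 7.2 |
|---|---|---|
| SAE | Related SAE: no further dose, follow-up continues | Any SAE: may be removed from the study |
| Pregnancy before Dose 2 | No further dose, follow-up continues | May be removed from the study |
| AE or laboratory abnormality | Bars dosing only through the general clinical grounds | May be removed only if staying is not in the subject's best interest |

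The first two rows need reconciling. Section 8.3.10 adds to the second: pregnancies are to be reported through Day 394 and followed to outcome.

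**The case against.** The strongest reply is that Section 7.1.3.1 only encourages continuation and forbids nothing after Day 366. Sections 7.1.4, 4.4 and 8.3.5 all point to Day 394, and the reference to the last vaccination looks like leftover two-dose wording. SAP Section 4.1 equates 12 months after the last vaccination with Day 394, which is true only with two doses. This stands: the fault is a contradiction between passages, and a reader who infers a settled cut-off at Day 366 goes beyond the documents.

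A reader might also infer that, with no routine visit between Day 209 and Visit 14, everything after Day 209 is lost: 394 − 209 = 185 days, about 47% of the period. The documents do not support that. Table 4 provides an Early Termination Visit and an Unscheduled Visit, both with an interim history, and Section 8.2 requires that history to cover changes since the last contact and to look for AESIs, MAAEs and NOCMCs. A subject leaving at Day 366 could be asked about the preceding 157 days.

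Nor does Section 7.2 let any AE remove a subject. The AE and laboratory item carries the best-interest test. The whole list is permissive and asks that removed subjects be followed per protocol where possible, and AEs are to be followed to resolution or stabilization if the subject agrees. Removal after Day 29 can also serve a purpose, because blood draws and, for some, leukapheresis continue. These points soften the SAE and pregnancy items but leave open whether a removed subject keeps the Day 394 schedule.

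Finally, Table 13 does not say that any of the four left the study or which rule was applied to them; one missed Dose 2 for quarantine. Section 12.2 reports no SAEs to the date of writing. No bias in the trial's data has been shown.

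**Conclusion.** The concern holds as an internal contradiction with a small numerical effect. For subjects without Dose 2, Section 7.1.3.1 gives Day 366, while Sections 4.4, 7.1.4 and 8.3.5 and the primary endpoint give Day 394. The calendar gap is 28 days (7.1%) per subject, for at most 4 of 120 subjects. It matters more than 0.24% of person-time suggests because three of the four stopped for an AE and the missed time falls in a primary safety endpoint. Separately, the unconditional SAE item and the pregnancy item in Section 7.2 do not fit with Sections 7.1.3.1 and 7.1.4.

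This rests on reading the last vaccination of a one-dose subject as Dose 1 on Day 1, on the protocol's own 365-day convention, and on a site acting on Section 7.1.3.1 or 7.2 rather than on the passages that point to Day 394.

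**What to change.** - **Section 7.1.3.1:** align the end of follow-up with Sections 4.4, 7.1.4 and 8.3.5, so that one-dose subjects are followed for safety through Visit 14 (Day 394) per the Schedule of Activities.
- **Section 7.2:** reconcile the SAE and pregnancy items with Sections 7.1.3.1 and 7.1.4, so that the event alone does not end safety observation for the Day 394 endpoint.
- **Unchanged:** the investigator's best-interest ground and every dosing contraindication. Altering those would be a clinical-management change beyond what the contradiction calls for.

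The cost is wording in two sections and attendance at visits already in the schedule. Section 12 carries main-study rules into the substudy unless it says otherwise, so the Section 7.2 clarification would also serve the endpoint that runs to Substudy Day 366.
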